9.3.5 Vaccine Efficacy (VE) Point Estimate

The VE point estimate will be calculated as:

• $100 \times [1 - (\lambda V / \lambda C)]$ (%)

where λV and λC denote the hazard rates from a Cox proportional hazards (CPH) model for the HIL-214 and placebo arms, respectively, and $\lambda V / \lambda C$ the hazard ratio.

9.3.6 Total Person-Time at Risk

Person-time will be calculated in days and converted to months by dividing by 30.4375.

9.3.6.1 Last Information Date (Censoring Date)

Censoring date for the primary and secondary efficacy endpoints is defined as the earlier of the last contact date, date of discontinuation from the study, and end of the primary observation period (determined individually for each subjects based on the timing of the second dose). Censoring date for exploratory endpoint analysis will be defined as for the primary and secondary endpoints but assessing the exploratory observation period instead of the primary observation period. For the endpoint of vaccine efficacy between first and second dose, censoring will consider an observation period ending the day before the second dose. AGE event date is defined as the derived date per Section 9.3.1.

9.3.6.2 Analysis of a Single Event

The total person-time at risk for the analysis of single events will be calculated by summing the subject level time up to censoring or the first event during the relevant observation period.

The subject-level time at risk in days is derived as:

Time at Risk
$$(Subject)_S = Date of Event or Censoring - Start Date of Relevant Observation Period + 1$$

See Sections 9.2.6 and 9.2.7 for details on the relevant observation period.

The person-days at risk for both trial arms is derived as:

Total PersonDays at Risk_s =
$$\sum$$
 Time at Risk (Subject)_s

If the start date of the relevant observation period is after the date of censoring, the person-days at risk for that subject is set to zero.

9.3.6.3 Analysis of Multiple Events

The total person-months at risk for the analysis of multiple events will be calculated by summing the subject level time at risk up to the last information date during the relevant observation period and after the last AGE event.

The subject level time at risk is derived as:

Time at Risk
$$(Subject)_M = Last Information Date - Start Date of Relevant Observation Period + 1$$

See Section 9.2.6 and 9.2.7 for details on the relevant observation period.

The study level person-days for both trial arms at risk is derived as:

Total PersonDays at Risk
$$_{M} = \sum$$
 Time at Risk (Subject)_M

9.3.7 Unadjusted Event Rate

The unadjusted event rate will be calculated as:

Number of Events during Relevant Observation Period / Total PersonDays at Risks

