9.3.9 Incidence Rate

The incidence rate during the relevant observation period will be defined as the number of:

Number of Subjects with Events during Relevant Observation Period / Total PersonDays at Risks

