11.5 Efficacy Analyses

11.5.1 Hypothesis Testing Strategy and Multiplicity Adjustments

The analysis for the primary efficacy endpoint will be performed at an alpha risk of 5% (two-sided). Statistical analysis of the key secondary efficacy endpoint will be performed only if the primary efficacy endpoint is significant.

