11.5.3.2 Supplementary Analysis

The following supplementary analyses will be performed for the primary efficacy endpoint:

- Analysis based on the PPS-E using the same definition of the AGE events and same statistical methods as for the primary endpoint analysis as described in sections 11.5.3 and 11.5.3.1.
- Analysis of multiple moderate or severe events per subject will be performed using the Andersen-Gill extension of the Cox model (Andersen & Gill, 1982), stratified by country similarly to the primary endpoint. Recurrent AGE events are described in Section 9.3.2 The total number of events, the total time at risk (see Section 9.3.6.3) and unadjusted event rate (see Section 9.3.7) will be presented. Vaccine efficacy will be derived and presented in the same way as the primary analysis in Section 11.5.3.1.

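### SAP 9.3.7 appears to divide all events by first-event person-time, so the recurrent-event rate in 11.5.3.2 will not match the events and time reported with it and will read slightly high

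*SAP*

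**What the plan says.** SAP 9.3.6 sets up two kinds of person-time.

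- **Single event (9.3.6.2, subscript S).** The total is obtained by "summing the subject level time up to censoring or the first event during the relevant observation period". A subject's clock stops at the first event.
- **Multiple events (9.3.6.3, subscript M).** The total is "calculated by summing the subject level time at risk up to the last information date during the relevant observation period and after the last AGE". In other words, the clock runs on past events to the last information date, which 9.3.6.1 caps at the end of the observation period.

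Two rates are then defined.

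- **Unadjusted event rate (9.3.7):** "Number of Events during Relevant Observation Period / Total PersonDays at Risks".
- **Incidence rate (9.3.9):** "Number of Subjects with Events during Relevant Observation Period / Total PersonDays at Risks".

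The numerators differ (events against subjects with events), but the denominators are written identically.

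For the Andersen-Gill analysis, 11.5.3.2 states: "The total number of events, the total time at risk (see Section 9.3.6.3) and unadjusted event rate (see Section 9.3.7) will be presented". On VE it adds: "Vaccine efficacy will be derived and presented in the same way as the primary analysis in Section 11.5.3.1".

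**The concern.** A rate that counts repeat events needs the time in which repeats can occur. With S as the denominator, a second event enters the numerator while the days in which it arose are left out. A subject with a single event also loses all later follow-up, although 9.3.6.3 treats that time as at risk for this analysis. S can never exceed M, so the error goes one way: the rate is too high, or at best equal.

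What is at stake is a reconciliation failure. Section 11.5.3.2 puts three linked quantities side by side: events, time and rate. Anyone who divides the first by the second will get a different answer from the third, in every arm where an event occurs before that subject's last information date. The result is an avoidable query on a supplementary efficacy output.

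**Working it through.** **The plan's own figures.** The documents give no value for the unadjusted event rate, so there is nothing to reproduce directly. The size check borrows its inputs from SAP 8.1: VE 70% (hazard ratio 0.30), a 6-month incidence of 3.5%, and 24 cases for power above 80%. At the SAP's two-sided 5% level (11.5.1), the Schoenfeld form gives z = sqrt(24) x |ln 0.30| / 2 - 1.960 = 2.949 - 1.960 = 0.989, hence power of 83.9%, in line with the stated figure. Other approximations are lower (Freedman 75.1%, exact conditional binomial 69.1%). The 24 cases serve here only as a low-count scenario.

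**Assumptions.** The 3.5% is taken as the placebo risk, which the SAP does not say. There are 1500 subjects per arm (SAP 8.0), a window T = 6 x 30.4375 = 182.6 days (9.2.6 and 9.3.6), a constant hazard in each arm, and recurrences at the same hazard. Dropout is left out because it shortens S and M about equally.

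**Formulas, per arm, with 6-month risk p.**

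- Cumulative hazard: h = -ln(1 - p)
- Expected events, all occurrences: 1500 x h
- M = 1500 x T
- S = 1500 x T x p / h
- Overstatement of the rate: M / S - 1 = h / p - 1

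**Results at the planned incidence.**

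| | Placebo | HIL-214 |
|---|---|---|
| p | 0.035 | 0.035 x 0.30 = 0.0105 |
| h | 0.03563 | 0.01056 |
| Expected events | 53.4 | 15.8 |
| M, person-days | 273,938 | 273,938 |
| S, person-days | 269,115 | 272,497 |
| Rate per 100 person-months, over M | 0.594 | 0.176 |
| Rate per 100 person-months, over S | 0.604 | 0.177 |
| Overstatement | 1.8% | 0.5% |

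The hand-check that would fail: M is 1500 x 6 = 9,000 person-months, and 53.4 / 9,000 = 0.594 per 100, against a reported 0.604.

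The gap hardly depends on repeat events. In placebo, 53.4 events against 1500 x 0.035 = 52.5 subjects with an event is about one repeat. Almost all of the gap comes from follow-up dropped after a first event.

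**If only 24 cases accrue.** Split at a hazard ratio of 0.30, placebo has 24 / 1.3 = 18.46 and HIL-214 has 5.54. With events on average mid-window, the overstatement is 1 / (1 - e / 3000) - 1, where e is the arm's case count and 3000 is 2 x 1500. This gives 0.62% and 0.18%.

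**Sensitivity to event timing at 3.5%.** Let f be the average share of the window remaining after a first event. The overstatement is 1 / (1 - p x f) - 1.

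- f = 0.25 (late events): 0.9% placebo, 0.3% HIL-214
- f = 0.5: 1.8%, 0.5%
- f = 0.9 (early events): 3.3%, 1.0%

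**Sensitivity to the meaning of 3.5%.** If it were the average over both arms, placebo risk would be 0.035 x 2 / 1.3 = 5.38% and HIL-214 risk 1.62%. At f = 0.5 the overstatement would be 2.8% and 0.8%.

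**Direction between arms (p = 3.5% in placebo, f = 0.5).** At a hazard ratio of 1 the overstatement is 1.8% in both arms. At 1.2 it is 1.8% in placebo and 2.1% in HIL-214.

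**The case against.** **The trailing s may not be a subscript.** In 9.3.6.2 and 9.3.6.3 the subscripts are explicit. In 9.3.7 and 9.3.9 the word simply ends in s, which could be a plural. The subscript reading is much the likelier: the same string closes 9.3.9, where S is the right denominator, and an M would not appear as an s. If it is only a plural, 9.3.7 leaves the choice between S and M open, and 11.5.3.2 hints at M by citing 9.3.6.3 for the time at risk. The defect would then be ambiguity rather than a wrong formula, but the same edit cures it.

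**A reader might infer that a VE estimate is inflated.** The documents do not support this. The primary VE comes from the stratified Cox model (11.5.3.1) and the recurrent-event VE from the Andersen-Gill model. The Poisson analysis (11.5.3.3) defines its own rate ratio, models each subject's log time at risk, and does not cite 9.3.7. One minus the ratio of the rates above would move from 70.4% over M to 70.7% over S, but no visible section plans that calculation.

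**A reader might infer that placebo is always overstated more.** That holds only if placebo has more events, as the design assumes. The last step of the working shows equality at a hazard ratio of 1 and reversal above it.

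**A reader might infer a larger problem for endpoints with higher incidence.** The arithmetic would allow it, but the only visible use of 9.3.7 is for the primary endpoint. The exploratory analyses are redacted and cannot be judged.

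It is also fair that no table shell is visible. That the three quantities appear together is inferred from the single sentence in 11.5.3.2.

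**Conclusion.** The point stands as a small error of definition. Followed as written, 9.3.7 gives a recurrent-event rate over first-event time. That rate will not equal the reported events divided by the reported time, and it is slightly too high. Under the design assumptions the excess is about 1.8% of the rate in placebo and 0.5% in HIL-214, falling to about 0.6% and 0.2% with 24 cases in total. These sizes rest on reading the denominator as S, on taking 3.5% as the placebo risk, on VE of 70%, and on events spread about evenly over the window. The reconciliation failure itself needs only the first of these. Descriptive rates alone are affected; no hypothesis test, planned VE or success criterion changes.

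**What to change.** In SAP 9.3.7, replace the denominator with Total PersonDays at Risk_M from 9.3.6.3. Keep Risk_S in 9.3.9, with the subscript clearly set in both formulas.

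In the same edit, state one unit for the time and the rate in 11.5.3.2. Section 9.3.6.3 speaks of person-months in its text and person-days in its formula, and 9.3.6 already supplies the conversion (30.4375 days per month).

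The cost is one subscript in the SAP and one line of table code. No objective, endpoint, alpha or model is touched.

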9.3.8 Time to Event (Days)

The time to an event or censoring during the relevant observation period for each subject will be derived as:

Time to [*Event*] (*Days*) = *Date of Event or Censoring* – *Start Date of Relevant Observation Period* + 1

If a subject's last contact date occurs before the start date of the observation period, the subject's time to event will be set to 0. See Section 9.2.6 and 9.2.7 for details on the relevant observation period.

9.3.9 Incidence Rate

The incidence rate during the relevant observation period will be defined as the number of:

Number of Subjects with Events during Relevant Observation Period / Total PersonDays at Risks

9.4 Safety

9.4.1 Adverse Events After Vaccine Doses

Unsolicited AEs will be summarized up to 28 days after each vaccine dose if:

 $1 \leq AE Start Date - Date of Vaccine Dose + 1 \leq 28$

Unsolicited adverse events starting after 28 days after the first dose of vaccine but before the second dose, or starting 28 days after second dose, will not be included in the safety summaries, but will be included in the listings.

9.4.2 Solicited Adverse Events

Solicited local AEs include Injection Site Pain, Erythema, Induration and Swelling, and solicited systemic AEs include Fever, Drowsiness, Irritability/Fussiness, Loss of Appetite, Vomiting and Diarrhea. Solicited AEs are collected at 30 minutes after vaccine dose and daily for 7 days starting on the day of vaccine dose.

9.5 Other Conventions

9.5.1 Values below the Lower Limit of Quantification (LLOQ)

For the immunogenicity lab concentrations, values that are below the lower level of detection (LLOD) will be set to 0.5 of the LLOD. Values between LLOD and LLOQ are set to mid-point of the interval between LLOD and LLOQ, and values above upper limit of quantification (ULOQ) are set to the ULOQ. The table in Appendix B displays the relevant LLOD and LLOQ values for each assay. The actual reported values will be provided in by-subject listings.

9.5.2 Seroresponse Rate

Seroresponse is defined as a 4-fold increase from baseline in anti-Nov antibody concentrations as measured by histo-blood group antigen (HBGA) blocking assay and pan-immunoglobulin enzyme-linked immunosorbent assay (pan-Ig), to GI.1 and GII.4 and to both GI.1 and to GII.4. If the baseline value is missing, seroresponse will not be calculated. Subjects without a seroresponse will be referred to as non-responders. The seroresponse rate is defined as the ratio of the number of subjects who met the seroresponse criteria, divided by the number of subjects in the relevant group in the analysis set.

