9.1.5 Immunogenicity Per-Protocol Analysis Set (PPS-I)

The PPS-I will include all subjects in the mFAS with a baseline blood sample collected before administration of first dose and who have no important protocol deviations which may affect evaluation of immunogenicity. These categories of important protocol deviations include: (1) not meeting selected entry criteria, (2) receiving wrong or incomplete trial product (3) receiving prohibited therapies, (4) protocol-described regimen not followed for storage of investigational vaccine or placebo, (5) vaccination regimen described in protocol not followed for administration of investigation vaccine or placebo, (e.g., administered out of window, or in incorrect injection site) and (6) other important protocol deviations that may affect evaluation of the immunogenicity. Subjects will be analyzed according to the trial vaccine which they actually received.

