9.2.5 Analysis Visit Windows

The study protocol describes the timing of visits and corresponding windows. Visits are not derived for statistical analysis. Measurements from unscheduled visits are excluded from all summaries.

For immunogenicity analysis on the PPS-I analysis set, the following windows will define which results are summarized. Immunogenicity assay results will be excluded if the corresponding blood sample is collected outside of the following windows:

- Visit 2 blood collection must be between 23 days and 70 days from dose 1 vaccination date, and also before second vaccination.
- Visit 3 blood collection must be between -10 and +33 days from 28 days after dose 2 vaccination date.
- Visit 4 blood collection must be between -17 and +40 days from subject's one year of age.
- Visit 5 blood collection must be between -17 and +40 days from subject's 18 months of age.
- Visit 6 blood collection must be between -17 and +40 days from subject's two years of age.

Summaries exclude data outside of allowable visit windows as described here. Data outside of allowable windows and data from unscheduled visits will be listed.

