9.5.3 Geometric Mean Concentration (GMC)

The GMC will be calculated as the anti-logarithm of \sum (log transformed concentration/n), i.e. as the anti-logarithm transformation of the mean of the log-transformed concentration, where n is the number of subjects with concentration information in the relevant group. The geometric standard deviation (GSD) will be calculated as the anti-logarithm transformation of the standard deviation of the log-transformed concentration. The 95% confidence interval (CI) for GMC will be calculated as the anti-logarithm transformation of the sample mean of the log-transformed concentrations.

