11.6 Secondary Immunogenicity Endpoint

11.6.1 Immunogenicity of HIL-214

The secondary immunogenicity endpoints for the trial are pan-Ig and HGBA blocking antibody concentrations. These endpoints will be summarized as seroresponse rates (see Section **9.5.3**), GMCs and GMFRs (see Section **9.5.4**) for HBGA blocking antibody concentrations and for pan-Ig antibody concentrations collected at Visit 1(Day 1), Visit 2 (28 to 56 days post dose 1 - prior to dose 2) and Visit 3 (28 days post, and when the subjects reach the age of 1 year (Visit 4), 18 months (Visit 5) and 2 years (Visit 6) (see Section **9.2.5**). These estimates will be presented by trial arm separately for GI.1 and GII.4 NoV genotypes. Summaries of results for Visits 1 through Visit 4 will be included in the primary and secondary efficacy analysis. 18 months (Visit 5) and 2 years (Visit 6) results will be summarized at the end of trial.

The number of subjects with seroresponse, seroresponse rate and 95% CI on post-dosing visits will be presented. The two-sided exact 95% CI will be estimated using the Clopper-Pearson exact method (Clopper CJ & Pearson ES, 1934). For details of the derivations of GMC and GMFR, see section 9.5.3. Longitudinal plots and reverse cumulative distribution plots for concentrations will be presented by genotype and trial arm. The secondary immunogenicity analyses will be performed on the FAS and the PPS-I.

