12.1.1 Solicited Adverse Events

The following summaries will be prepared for each trial arm and overall after each dose of trial vaccine and after any dose:

- The number and percentage of subjects experiencing solicited local and systemic AEs; overall and by severity
- The number and percentage of subjects experiencing local and systemic AEs, for each of 7 days after vaccination; overall and by severity
- The number and percentage of subjects experiencing solicited local and systemic AEs by day of onset
- The number and percentage of subjects experiencing solicited systemic AEs by relationship to vaccine as determined by the clinical investigator.

Only solicited AEs collected up to 7 days after dosing of vaccine will be summarized. Percentages will be based on the number of subjects who had at least one non-missing assessment for a given event.

Solicited safety data collected 30 min post-vaccination will be summarized separately.

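### The SAP's seroresponse denominator counts every subject in the arm, so a missing or excluded result is scored as non-response; the GMFR divisor and the GMC confidence-interval sentence also need correcting

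*SAP*

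**What the plan says.** SAP 9.5.2 defines seroresponse as a 4-fold rise from baseline. The rate is the number of responders "divided by the number of subjects in the relevant group in the analysis set". On missing data it has one rule: "If the baseline value is missing, seroresponse will not be calculated". It then adds: "Subjects without a seroresponse will be referred to as non-responders".

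The other relevant provisions are:

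- **SAP 9.5.3 (GMC):** the divisor n is limited to subjects with data: "where n is the number of subjects with concentration information in the relevant group". The 95% CI is described as the antilog of the sample mean of the log concentrations.
- **SAP 9.5.4 (GMFR):** the GMFR is the geometric mean of the post-dose to baseline ratios, but the formula divides the sum of log ratios by the count of subjects in the relevant group. Its CI follows the GMC method.
- **SAP 9.1.2 (FAS):** at least one dose; no blood sample is required.
- **SAP 9.1.5 (PPS-I):** "The PPS-I will include all subjects in the mFAS with a baseline blood sample collected" before the first dose, with no important deviations; no post-dose sample is required.
- **SAP 9.2.5 (PPS-I windows):** "Immunogenicity assay results will be excluded if the corresponding blood sample is collected outside of the following windows". The result is dropped, not the subject.
- **SAP 11.6.1:** "The number of subjects with seroresponse, seroresponse rate and 95% CI on post-dosing visits will be presented", with Clopper-Pearson limits, on the FAS and PPS-I. It refers the reader to 9.5.3 for the SRR, but 9.5.3 contains no SRR rule.

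**The concern.** Three groups of subjects have no evaluable seroresponse status at a visit: those with no baseline (FAS only, since the PPS-I requires a baseline sample), those with no post-dose result (either set), and those whose result is excluded as out of window (PPS-I only). Section 9.5.2 removes none of them from the denominator. It says only that the status is not calculated when baseline is missing, and it is silent on the other two groups.

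Followed literally, the SRR then mixes immune response with data completeness. Results are planned at five post-dose visits (Visits 2 to 6). If attrition grows towards Visits 4 to 6, a falling SRR could be read as waning antibody. Unequal attrition between arms would bias the comparison of arms. The SRR would also use a different n from the GMC beside it, and the FAS and PPS-I could differ only because of missing samples.

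**Working it through.** The plan states no SRR, GMFR or expected serology missingness, so there is no figure of its own to reproduce. The check has a textual part and an illustrative part.

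**Does the phrase in 9.5.2 already mean subjects with results?** Sections 9.5.2 and 9.5.3 both use the term relevant group. Section 9.5.3 adds the condition of having concentration information, which would be redundant if the term alone carried it. Section 12.1.1 likewise states its restriction for solicited events: "Percentages will be based on the number of subjects who had at least one non-missing assessment for a given event". The FAS and PPS-I definitions do not supply the restriction, and 11.6.1 points to a section without an SRR rule. So 9.5.2 is the only stated denominator, and it is unrestricted.

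**SRR as written.** Inputs: N = 1500 per arm (SAP 8.0). Assumed: true SRR p of 50%, 70% or 90%; share without an evaluable result m of 10%, 20% or 30%; missingness unrelated to response.

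Responders = p × N(1 − m), so reported SRR = p × N(1 − m) / N = p(1 − m).

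| True SRR | m = 10% | m = 20% | m = 30% |
|---|---|---|---|
| 50% | 45% | 40% | 35% |
| 70% | 63% | 56% | 49% |
| 90% | 81% | 72% | 63% |

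Clopper-Pearson 95% limits at m = 10%, where 1500 × 0.9 = 1350 subjects are evaluable:

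| True SRR | As written | Evaluable denominator |
|---|---|---|
| 50% | 675/1500: 42.5–47.6% | 675/1350: 47.3–52.7% |
| 70% | 945/1500: 60.5–65.4% | 945/1350: 67.5–72.4% |
| 90% | 1215/1500: 78.9–83.0% | 1215/1350: 88.3–91.5% |

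Every interval as written excludes the true rate. With responders rounded to whole subjects, the upper limit first falls below the true rate at 78 missing (78/1500 = 5.2%) for 50%, 51 (3.4%) for 70% and 27 (1.8%) for 90%.

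**Unequal missingness.** With a true SRR of 80% in both arms and 10% versus 20% missing, the rates as written are 0.8 × 0.9 = 72% and 0.8 × 0.8 = 64%: an 8-point difference where none exists.

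**GMFR divisor taken literally.** The sum of log ratios over N(1 − m) subjects, divided by N, gives (1 − m) × mean log ratio, so reported GMFR = GMFR^(1 − m). Each missing ratio is in effect set to 1.

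| True GMFR | m = 10% | m = 20% | m = 30% |
|---|---|---|---|
| 0.8 | 0.82 | 0.84 | 0.86 |
| 1 | 1 | 1 | 1 |
| 2 | 1.87 | 1.74 | 1.62 |
| 5 | 4.26 | 3.62 | 3.09 |
| 10 | 7.94 | 6.31 | 5.01 |

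**GMC interval.** Section 9.5.3 gives the GMC as antilog(mean of logs), and the 95% CI as the same expression. With no standard error term, the sentence yields a single point. Section 9.5.4 carries this over to the GMFR.

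**The case against.** The strongest reply is that the relevant group is never defined and could be meant as subjects with results. A subject whose status is not calculated is naturally neither responder nor non-responder, and no sentence states outright that missing equals non-response. SAP 12.1.3 uses the whole safety set as its denominator, so the SAP uses both conventions. If the full set is intended here, scoring missing as non-response is a recognised conservative choice.

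The intention may well be evaluable subjects. But a programmer following 9.5.2 literally would use the full set, and the added condition in 9.5.3 tells against reading the restriction into the phrase. If missing-as-non-response is intended, the SAP should say so and label it.

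Other points carry weight:

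- The GMFR definition, and the pointer in 11.6.1 to 9.5.3 for its derivation, make the literal divisor unlikely to be programmed. The GMFR figures show an internal contradiction more than a probable result.
- The interval sentence has an obvious intended meaning.
- The PPS-I windows are wide (Visit 3: −10 to +33 days; Visits 4 to 6: −17 to +40 days), so losses to out-of-window sampling may be small.
- Responder counts are reported with the rate, so a careful reader could recover the denominator.
- The secondary endpoint table stops at 28 days post dose 2, so the waning scenario concerns visits beyond it, although 11.6.1 does summarize them.

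**Conclusion.** The concern holds. As written, 9.5.2 gives an SRR of p(1 − m), not p, and the SAP has no other SRR denominator. The size depends on serology missingness, which the documents do not give. The 20–30% for drop-out and non-evaluable samples in SAP 8.1 belongs to the efficacy sample size, and applying it to serology would be an assumption. Under the assumptions above, 1.8% to 5.2% missing is enough for the interval to exclude the true rate. The 9.5.4 divisor and the 9.5.3 interval sentence are wording errors with a clear intended meaning. The effect is confined to descriptive summaries of a secondary objective; the primary efficacy analysis, the testing sequence and the sample size are untouched. It should be fixed.

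**What to change.** 1. In SAP 9.5.2 and 9.5.4, define n separately for each visit and assay as subjects in the arm with a non-missing baseline and an evaluable post-dose result (in window for the PPS-I), and show that n in each table.
2. In 9.5.3, and by reference in 9.5.4, state the 95% CI as antilog(mean of logs ± t(0.975, n − 1) × SD/√n), with the mean and SD on the log scale.
3. In 11.6.1, correct the SRR cross-reference to 9.5.2.
4. If missing-as-non-response is wanted, keep it as a labelled sensitivity analysis.

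The cost is a few sentences in the SAP and one n column per visit. No new data are needed, and the efficacy analyses do not change.
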